#### **12.1.1.2. Serious Adverse Event**

A SAE is an adverse event/reaction that results in any of the following outcomes:

- Death
- Is life-threatening (subject is at immediate risk of death at the time of the event; it does not refer to an event that hypothetically might have caused death if it were more severe)
- Requires subject hospitalization (formal admission to a hospital for medical reasons) or prolongation of existing hospitalization
- Results in persistent or significant disability/incapacity (i.e., there is a substantial disruption of a person's ability to carry out normal life functions)
- Is a congenital anomaly/birth defect

Important medical events that may not result in death, are not life-threatening, or do not require hospitalization may be considered a SAE when, based upon appropriate medical judgment, they may jeopardize the subject's health or may require medical or surgical intervention to prevent one of the outcomes listed in this definition. Examples of such events may include allergic bronchospasm requiring intensive treatment in an emergency room or at home, blood dyscrasias, or convulsions that do not result in subject hospitalization.

In addition, the sponsor considers any abortions (elective or spontaneous), fetal demise, and still birth to be serious adverse events for reporting purposes (see Section 12.1.6).

Overdose will be considered an SAE only if any of the seriousness criteria are met. Any clinical complication in association with the overdose should be reported as an AE or SAE (as applicable) along with the overdose (see Section 12.2.2). Details of signs or symptoms, clinical management and outcome should be reported, if available. Overdose without associated signs or symptoms should not be recorded as AEs but should be recorded as protocol deviations.

#### **12.1.1.3. Adverse Events of Special Interest**

For this protocol, nonserious treatment-emergent rashes will be considered events of special interest. This event in and of itself will not be considered serious unless it meets the criteria above. Events of rash regardless of severity or suspected relationship to study drug/IMP must be reported to the Sponsor Medical Monitor as described in Section 12.1.5.1. Management of rash possibly, probably or definitely suspected to be related to study drug/IMP, is provided in Section 12.2.1.

#### **12.1.2. Method, Frequency, and Time Period for Detecting Adverse Events and Reporting Serious Adverse Events**

Reports of all AEs and SAEs, regardless of Investigator attribution, are to be collected from the time of signing of the informed consent. All AEs and SAEs are to be reported on the AE eCRF.

AEs should be documented on eCRFs as Investigators become aware of them. AEs are to be followed until the event resolves. If an event is ongoing at the last follow-up visit, Grade 1 and 2 events do not need to be followed if the event is deemed unlikely to be related or not related to study drug/IMP (see Section 12.1.3 for AE grading). For all Grade 3 and 4 events or events deemed possibly, probably or definitely related to use of study drug/IMP, the event should be followed until the AE is resolved or the subject is in a clinically stable condition with regards to the AE.

The Investigator shall report all SAEs immediately to the Sponsor by communicating with the Medical Monitor (phone or email) and by submission of an SAE report form via fax or email, and entering the event onto the AE eCRF within 24 hours of their knowledge of the event (see Section 12.1.5). The SAE report form is a detailed, written report on the SAE provided by the Sponsor or designee. The Investigator should follow all unresolved SAEs observed during the study until they are resolved, or are judged medically stable, or are otherwise medically explained.

The Investigator should attempt, if possible, to establish a diagnosis based on the presenting signs and symptoms. In such cases, the diagnosis should be documented as the AE and not the individual sign/symptom. If a clear diagnosis cannot be established, each sign and symptom must be recorded individually. Once a diagnosis is made during evaluation or treatment, the Investigator will update the AE record with this diagnosis. The immediate and follow-up reports shall be sent to the Sponsor within 24 hours to ensure that the Sponsor shall have the necessary information to continuously assess the benefit-risk profile of the study drug/IMP in clinical trial.

### 12.1.3. Definition of Severity

All AEs will be assessed (graded) for severity and classified using the Division of Microbiology and Infectious Diseases (DMID) criteria for grading AEs (see Appendix 16.1). Any AEs not covered by the DMID criteria will be assessed and classified into 1 of 4 clearly defined categories as follows:

- |                          |   |
|--------------------------|---|
| Mild:             | (Grade 1): Transient or mild symptoms; no limitation in activity; no intervention required. The AE does not interfere with the participant's normal functioning level. It may be an annoyance.  |
| Moderate:         | (Grade 2): Symptom results in mild to moderate limitation in activity; no or minimal intervention required. The AE produces some impairment of functioning, but it is not hazardous to health. It is uncomfortable or an embarrassment. |
| Severe:           | (Grade 3): Symptom results in significant limitation in activity; medical intervention may be required. The AE produces significant impairment of functioning or incapacitation.  |
| Life-threatening: | (Grade 4): Extreme limitation in activity, significant assistance required; significant medical intervention/therapy required to prevent death, hospitalization or hospice care probable.   |

#### 12.1.4. Definition of Relationship to Study Drug (Investigational Medicinal Product)

The Investigator or medically qualified designee must review each AE and make the determination of relationship to study drug/IMP using the following guidelines:

Not Related:	The event can be readily explained by other factors such as the subject's underlying medical condition, concomitant therapy, or accident, and no temporal relationship exists between the study drug/IMP and the event.
Unlikely:	The event does not follow a reasonable temporal sequence from drug administration and is readily explained by the subject's clinical state or by other modes of therapy administered to the subject.
Possibly Related:	There is some temporal relationship between the event and the administration of the study drug/IMP and the event is unlikely to be explained by the subject's medical condition, other therapies, or accident.
Probably Related:	The event follows a reasonable temporal sequence from study drug/IMP administration, abates upon discontinuation of the study drug/IMP, and cannot be reasonably explained by the known characteristics of the subject's clinical state.
Definitely Related:	The event follows a reasonable temporal sequence from study drug/IMP administration, follows a known or suspected response pattern to the study drug/IMP, is confirmed by improvement upon stopping the study drug/IMP (dechallenge), and reappears upon repeated exposure (rechallenge, if rechallenge is medically appropriate).

#### 12.1.5. Reporting Serious Adverse Events and Suspected Unexpected Serious Adverse Reactions

Any SAE must be reported by phone or email to the Sponsor Medical Monitor and in writing via email or fax using the SAE/Event of Special Interest report form within 24 hours of the Investigator's awareness of the SAE. In addition, all SAEs must be recorded on the AE eCRF in real time. All additional follow-up evaluations of the SAE must be reported to BioCryst or its designee as soon as they are available. The SAE report forms should be sent to the following email addresses or fax numbers:

[name], Medical Monitor

Cell number (24 hours) [contact]

Email: [[contact]](mailto:[contact]); [[contact]](mailto:[contact])

Safety [contact]

Immediate reporting should allow BioCryst to take the appropriate measures to address potential new risks in a clinical trial. Therefore, the initial report should be submitted by the Investigator within a very short period of time and under no circumstances should this period exceed 24 hours following awareness of the SAE.

The follow-up report should allow BioCryst to determine whether the SAE requires a reassessment of the benefit-risk profile of the study drug/IMP in clinical trial, if the relevant information was not already available and provided in the initial report.

Investigators or designees at each site are responsible for retaining copies of all SUSAR reports (initial and follow-up) and other safety information (e.g., revised IB) in their files.

BioCryst or its designee will submit all SUSAR reports (initial and follow-up) or other safety information (e.g., revised IB) to the IEC and central IRBs.

BioCryst shall ensure that all relevant information about SUSARs that are fatal or life-threatening is recorded and reported as soon as possible to all competent authorities, and to the IECs, and central IRBs, in any case no later than 7 calendar days after knowledge by BioCryst of such a case, and that relevant follow-up information is subsequently communicated within an additional 8 days. All other SUSARs shall be reported to the competent authorities concerned and to the IECs/IRBs concerned as soon as possible but in no case later than 15 calendar days of first knowledge by BioCryst. BioCryst or designee shall also inform all Investigators.

#### **12.1.5.1. Reporting Events of Special Interest**

Although not an SAE, all events of treatment-emergent rash regardless of severity or suspected relationship to study drug/IMP must be reported by phone or email to the Sponsor Medical Monitor and in writing via email or fax using the SAE/Event of Special interest report form within 24 hours of the Investigator's assessment of the event. In addition, the event must be recorded on the AE CRF in real time. All additional follow-up evaluations of the event must be reported to BioCryst or its designee as soon as they are available. The SAE/Event of Special Interest report form should be sent to the following email addresses or fax numbers:

[name], Medical Monitor  
Cell number (24 hours) [contact]  
Email: [[contact]](mailto:[contact]); [[contact]](mailto:[contact])  
Safety [contact]

Immediate reporting should allow BioCryst to take the appropriate measures to address potential new risks in a clinical trial. Therefore, the initial report should be submitted by the Investigator within a very short period of time and under no circumstances should this period exceed 24 hours following awareness of the event. This also allows the independent DMC to review the emerging safety data in real time. In addition, the report form will allow a full clinical description and information regarding the evaluation that cannot be documented in the EDC due to free text limitations.

The follow-up report should contain information about the clinical course, medical evaluation, photographs, biopsy, and laboratory results.

#### **12.1.6. Pregnancy**

Any female subject who becomes pregnant during the course of the study should have study drug/IMP discontinued immediately and must be followed through the end of the pregnancy. While pregnancy is not considered an AE, all cases of fetal drug exposure via the parent as a study participant (including partners of study participants) are to be reported immediately to BioCryst or its designee. Consent from study partners will be obtained prior to reporting any details of the pregnancy. Information related to the pregnancy must be given on a "Pregnancy Confirmation and Outcome" form that will be provided by the Sponsor or its designee so that the

pregnancy may be followed and an outcome determined. Any AEs or SAEs experienced by a pregnant subject are to be reported as directed in Section 12.1.2 and Section 12.1.5. Any complications reported in a subject's pregnant partner should be reported on the Pregnancy Confirmation and Outcome form. All pregnancies must be followed to outcome which occurs when an infant is delivered (live or still born), there is fetal demise, or there is an abortion (spontaneous or induced). Abortion (spontaneous or induced), fetal demise, and still birth along with congenital abnormalities in the newborn, should be reported as separate SAEs.

#### **12.1.7. Serious Breaches**

It is the responsibility of the Sponsor to notify the licensing authority of any serious breach which is likely to effect, to a significant degree, the safety or mental integrity of the subjects of the study or the scientific value of the study. All serious breaches will be notified to the relevant competent authority within 7 days. The reporting to the Sponsor will be performed by the party who suspects the serious breach.

#### **12.1.8. Treatment Interruptions**

Treatment interruptions as a result of Investigator management of AEs potentially related to study drug/IMP are permissible. Resumption of study drug/IMP administration is also permissible upon resolution of the event as assessed by the Investigator and provided a plan for stringent monitoring of the subject for recurrence of the AE as appropriate. In addition, other extenuating circumstances may lead to treatment interruptions such as vomiting during an abdominal HAE attack or required fasting for medical procedures; in these cases, study drug/IMP should be resumed once the extenuating circumstance is resolved.

The Sponsor Medical Monitor should be notified in the event of a treatment interruption due to an AE. Any treatment interruption will be recorded in the eCRF and source documents, including the reason for the interruption.

#### **12.1.9. Emergency Procedures**

Access to study drug/IMP assignment will be available if the Investigator deems it necessary to break the study blind in the interest of a subject's medical safety, in case of a medical emergency, to meet regulatory reporting obligations, or if warranted during scheduled safety reviews. Where medically appropriate, the Investigator will contact the Sponsor Medical Monitor to discuss the situation which has arisen and resulted in the need for unblinding of the subject. The Sponsor Medical Monitor will not be involved in the decision to unblind.

Detailed instructions for unblinding will be provided in a separate communication to the sites.

### **12.2. Toxicity Management**

The Investigator (or qualified designee) will grade clinically significant events and laboratory abnormalities (if considered AEs) according to that detailed in Section 12.1.3. Grade 3 and 4 clinically significant laboratory abnormalities should be confirmed by repeat testing and before any contemplated study drug/IMP discontinuation, unless such a delay is not consistent with good medical practice.

In the event that 2 subjects experience similar Grade 3 or 4 treatment-emergent laboratory abnormalities or AEs that are suspected to be drug related as determined by the Investigator and not otherwise physiologically explained, a DMC meeting will be immediately convened by the Sponsor. Based on the data presented, a decision will be made as to whether to halt the study, to continue dosing, or to continue dosing with provisions introduced into the protocol via substantial amendment.

#### **12.2.1. Rash**

Management of rash should be based on best medical practice and address the subject's presentation. If a subject experiences a Grade 2 or higher rash suspected to be due to study drug/IMP, the subject should have study drug/IMP stopped as per Section 8.3.2.2.

In the event that 2 subjects experience a rash that is suspected to be study drug/IMP related as determined by the Investigator and not otherwise physiologically explained, a DMC meeting will be convened by the Sponsor. Based on the data presented, a decision will be made as to whether to halt the study, to continue dosing, or to continue dosing with provisions introduced into the protocol via substantial amendment.

Special evaluation of drug rash is required as per Section 11.1.12 and special reporting is described in Section 12.1.5.1.

#### **12.2.2. Overdose**

To date there is no experience with overdose of oral BCX7353. Single doses of up to 1000 mg, 7 days of dosing up to 500 mg/day, and 14 days of dosing with 350 mg/day revealed no clinically significant safety concerns in healthy subjects in Study BCX7353-101.

In the event that study personnel become aware of an overdose of study drug/IMP (> 3 capsules per calendar day) that is associated with an AE, both the overdose and the resultant event should be reported as AEs. Overdose without any symptoms (i.e., AEs) does not need to be reported as an AE. If overdose occurs with or without associated AEs, subjects should undergo clinical and laboratory monitoring as appropriate for their clinical condition and, if indicated, should receive clinically-indicated supportive therapy.

Additional information about overdose as an AE or SAE is discussed in Section 12.1.1.2.

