## 9. TREATMENT OF SUBJECTS

### 9.1. Description of Study Drug

BCX7353 is an oral small molecule inhibitor of plasma kallikrein. All subjects will receive 28 days of BCX7353 capsules or matching placebo for oral administration at one of the following doses:

- BCX7353 placebo QD orally (Parts 1, 2, 3 and 4)
- BCX7353 350 mg QD orally (Part 1)
- BCX7353 250 mg QD orally (Parts 2 and 3)
- BCX7353 175 mg QD orally (Part 4, if conducted)
- BCX7353 125 mg QD orally (Parts 2 and 3)
- BCX7353 62.5 mg QD orally (Part 3; Part 4 if conducted)

The study drug in this study consists of BCX7353 and placebo capsules. The active ingredient for this study is BCX7353, supplied by BioCryst. BCX7353 is a white to tan powder.

The BCX7353 capsules will be provided as hydroxypropyl methylcellulose (HPMC), size 00, opaque capsules. In Parts 1 and 2, capsules will be filled with drug substance to correspond to one-third of the total daily assigned treatment dose. Three capsules of BCX7353 will be administered orally QD for 28 days. In Parts 3 and 4, capsules will be filled with drug substance to correspond to one-half of the total daily assigned treatment dose. Two capsules of BCX7353 will be administered orally QD for 28 days.

The matching placebo will also be provided as HPMC, size 00, opaque capsules to match the BCX7353 capsules. The matching placebo will contain microcrystalline cellulose. Three capsules (Parts 1 and 2) or two capsules (Parts 3 and 4) of matching placebo will be administered orally QD for 28 days.

Additional details for the chemical and physical characteristics of BCX7353 may be found in the IB.

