### 9.2. Description of Study Drug Packaging, Labeling, and Storage.

Parts 1 and 2: The study drug will be packaged in bottles of 27 capsules per bottle and each kit will contain 2 bottles of study drug.

Parts 3 and 4: The study drug will be packaged in bottles of 32 capsules per bottle and each kit will contain 1 bottle of study drug.

Each kit will be labeled with the information required per local law and may include: Sponsor name, study protocol number, description of the contents, a statement regarding the investigational (clinical trial) use of the study drug, expiry date and kit treatment number.

Study drug will be stored between 15°C–25°C (room temperature).

Further details on the study drug will be provided in the study drug manual.

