#### **9.4. Study Drug (Investigational Medicinal Product) Administration and Treatment Compliance**

Subjects will take all study drug doses at home with the exception of study drug that will be administered under Investigator (or designee) supervision during scheduled on-treatment clinic visits on Days 1, 14 and 15 (and Day 28 if applicable). Subjects will be instructed to take 3 capsules (Parts 1 and 2) or 2 capsules (Parts 3 and 4) of study drug orally QD in the morning for 28 days. Subjects will be instructed to take study drug with food, or within 30 minutes after consuming food. On Days 1, 14 and 29, subjects should fast for 8 hours prior to their blood draw for laboratory testing.

The first dose of study drug will be administered in the clinic on Day 1. For study Days 14 and 15, subjects should be instructed to refrain from taking study drug prior to their visit to obtain a trough and/or serial blood draws at steady state.

On in-clinic dosing days (Days 1, 14 and 15), subjects will be required to consume food within 30 minutes prior to dosing (but after any blood draws for safety laboratory testing); the requirements for type and amount of food is to be provided to the subject (e.g., number of

servings of protein, carbohydrate, and/or fat) will be communicated in a separate document. On all other days, subjects should take the study drug in the morning with food (or within 30 minutes after consuming food). It is recommended that the study drug be administered with food in order to help minimize gastrointestinal effects. If gastrointestinal-related symptoms are noted as an AE, the site should query the subject and record whether the drug is being taken as instructed (i.e., with food).

Subjects will be instructed to maintain approximately the same daily dosing interval between study drug doses. If a subject forgets to take the study drug at the correct time, the dose may be taken later in the day; however, no more than 1 dose of BCX7353 should be taken on any calendar day. The subject should resume the standing regular dosing schedule on the next day.

Subjects will be instructed to record in their diary the time of day study drug was taken, and the number of capsules of study drug taken.

Subjects will be instructed to bring all drug kits (including both unused and used kit bottles) and diaries with them for each study visit. Accountability and adherence will be reviewed at each clinic visit.

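### The overdose threshold of more than 3 capsules a day fits Parts 1 and 2 only; in Parts 3 and 4 it leaves a day at 1.5 times the assigned dose outside the definition.

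*Protocol*

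**What the plan says.** Protocol 12.2.2 (Overdose) requires that when staff learn of "an overdose of study drug/IMP (> 3 capsules per calendar day) that is associated with an AE", both the overdose and the resulting event be reported as AEs. It adds that subjects who overdose, with or without symptoms, should be monitored as their condition requires. The count carries no Part qualifier.

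Protocol 12.1.1.2 deals with the symptom-free case: "Overdose without associated signs or symptoms should not be recorded as AEs but should be recorded as protocol deviations". It gives no capsule count and points the reader to 12.2.2.

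The regimen differs by Part. Under Protocol 9.1, "In Parts 1 and 2, capsules will be filled with drug substance to correspond to one-third of the total daily assigned treatment dose", whereas "In Parts 3 and 4, capsules will be filled with drug substance to correspond to one-half of the total daily assigned treatment dose". For the later Parts the same section states: "Two capsules of BCX7353 will be administered orally QD for 28 days". Protocol 9.4 gives the instruction to subjects as "3 capsules (Parts 1 and 2) or 2 capsules (Parts 3 and 4) of study drug orally QD".

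The SAP contains no overdose definition.

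**The concern.** A threshold of more than three capsules has an obvious meaning when three are assigned: anything above the daily dose. When the regimen changed to two capsules the number stayed at three, and no reason is given for a looser rule in the later Parts.

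The count matters because sites are blinded to treatment (Protocol 9.3.1) and cannot apply a threshold in milligrams. As written, a three-capsule day in Parts 3 or 4 does not trigger three steps:

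- reporting the overdose as an AE next to an associated event (12.2.2);
- recording a symptom-free overdose as a protocol deviation under that label (12.1.1.2);
- the monitoring instruction in 12.2.2.

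At stake is complete and consistent capture of excess dosing across Parts. The efficacy comparison is not affected.

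**Working it through.** **Inputs**

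- Threshold: more than 3 capsules per calendar day, all Parts (Protocol 12.2.2).
- Assigned capsules per day: 3 in Parts 1 and 2; 2 in Parts 3 and 4 (Protocol 9.1, 9.4).
- Doses: 350 mg (Part 1); 125 and 250 mg (Part 2); 62.5, 125 and 250 mg (Part 3); 175 mg, possibly with 62.5 mg (Part 4) (Protocol 9.1).
- Planned numbers: 20 in Part 3 at 1:3:3:3; 14 at 1:6 or 20 at 1:6:3 in Part 4 (Protocol 9.3.2).
- Supply in the later Parts: "The study drug will be packaged in bottles of 32 capsules per bottle and each kit will contain 1 bottle of study drug" (Protocol 9.2), one kit per 14 days (Protocol 9.3.2).

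**Where the plan's figure comes from.** The rule of more than the assigned count gives more than 3 with three capsules assigned, which reproduces 12.2.2 for Parts 1 and 2. With two assigned it gives more than 2, which does not match.

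**Multiple of the assigned dose** = capsules taken ÷ capsules assigned.

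| Parts | 3 capsules | Overdose as written? | 4 capsules | Overdose as written? |
|---|---|---|---|---|
| 1 and 2 | 3/3 = 1.00 | no | 4/3 = 1.33 | yes |
| 3 and 4 | 3/2 = 1.50 | no | 4/2 = 2.00 | yes |

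**Amount taken in Parts 3 and 4** = capsules taken × (assigned dose ÷ 2).

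| Assigned dose | Per capsule | 3 capsules (not classed) | 4 capsules (first classed) |
|---|---|---|---|
| 250 mg | 125 mg | 375 mg | 500 mg |
| 175 mg | 87.5 mg | 262.5 mg | 350 mg |
| 125 mg | 62.5 mg | 187.5 mg | 250 mg |
| 62.5 mg | 31.25 mg | 93.75 mg | 125 mg |

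Only 375 mg exceeds the 350 mg a day used in Part 1. It is below the 500 mg a day for 7 days that 12.2.2 reports as giving no clinically significant safety concern in healthy subjects.

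**Subjects who could be affected (a ceiling).** Part 3, active arms: 20 × 9/10 = 18, of whom 20 × 3/10 = 6 are at 250 mg. Part 4, if run: 14 × 6/7 = 12, or 20 × 9/10 = 18. Only those who take exactly three capsules on some day fall in the gap.

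**Supply.** Need per kit: 14 × 2 = 28. Spare: 32 − 28 = 4 capsules, so an extra-capsule day is physically possible.

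**The case against.** The strongest reply is that little is lost. Protocol 9.4 already says "no more than 1 dose of BCX7353 should be taken on any calendar day", and one dose in Parts 3 and 4 is two capsules. A third capsule is therefore a dosing departure that the data review meeting in SAP 11.2 could classify. Any clinical event is reported regardless (Protocol 12.1.2). Diary counts and accountability are reviewed at clinic visits, and liver tests or full chemistry are scheduled on Days 7, 14, 21 and 29. The 12.2.2 monitoring instruction sets no fixed test or timing. In absolute terms the gap is also small: at the top dose of each regimen, the first intake that counts is 4 × 350/3 = 467 mg in Part 1 and 500 mg in Part 3, and the largest that does not count is 350 mg against 375 mg.

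Most of this stands, and it is why the point is minor. It does not remove the inconsistency. The one-dose instruction does not call an excess an overdose and triggers nothing in 12.2.2. Section 12.1.1.2 refers overdose to 12.2.2, which holds the only count, so a site looking for the definition finds the wrong number for Parts 3 and 4.

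The planned compliance figure is also a weak backstop. SAP 11.2 names only compliance below 80% as a major deviation. SAP 12.3 multiplies dosing days by 3 to get expected capsules, although the SAP covers Part 3. A Part 3 subject who used both full kits over 28 days would score 64/(28 × 3) = 76%, when true compliance is 64/(28 × 2) = 114%.

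The safety comfort comes from healthy subjects. In HAE subjects at the interim, all seven Grade 3 treatment-emergent events and all three discontinuations for adverse events were at 350 mg (Protocol 5.3.3.1), just under 375 mg. Against that, one three-capsule day is a single-day excess, not 28 days of dosing.

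**Conclusion.** The point holds as a minor internal inconsistency in a safety definition. In Parts 3 and 4 a three-capsule day, 1.5 times the assigned dose and up to 375 mg, is not an overdose as written. The first classified intake is 2.0 times the dose there, against 1.33 times in Parts 1 and 2.

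At most 18 active-arm subjects in Part 3, and 12 or 18 in a conditional Part 4, could be affected. The documents do not suggest that any such day occurred. No planned efficacy or safety analysis, sample size or error rate changes.

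The conclusion assumes that the count in 12.2.2 is the operative definition for the whole protocol. No other count is given, and the cross-reference from 12.1.1.2 supports that reading.

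**What to change.** In Protocol 12.2.2, replace the fixed count with: *more than the assigned daily number of capsules (> 3 in Parts 1 and 2; > 2 in Parts 3 and 4) per calendar day*. Section 12.1.1.2 then needs no edit, because it refers to 12.2.2.

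Tell sites by memo and carry the wording into the next amendment. The sponsor handled weekly liver monitoring that way, by memo and then Amendment 2 (Protocol 5.4.4.2). The cost is one sentence and a memo, with no new procedures, visits or analyses. A protocol change must still be documented as an amendment, with ethics committee approval where necessary (Protocol 14.1.2), so it is cheapest combined with other changes. Part 3 was ongoing and Part 4 not yet started when this protocol version was written, so the change would apply to subjects still to be dosed.
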